Appendix 2. Criteria for Training Approval without Sponsor Review

Rating Scale	Educational Level*	Prior Clinical and Pediatric Experience	Prior Scale Experience
C-SSRS	MD or DO; PhD in Clinical or Counseling Psychology; RN or Master's level degree in a medical, social work, or mental health field	≥1 year clinical experience with pediatric population and/or pediatric clinical trial experience	Prior training with C-SSRS within the past two years with valid documented certification will exempt rater from having to retake C-SSRS training
YMRS	Child and Adolescent Psychiatrist (or in the case of countries outside the US, the local country equivalent in education and training) or Adult Psychiatrist (PI or SubI) or Doctoral Level Psychologist	≥1 year clinical experience with pediatric population and/or pediatric clinical trial experience	5 administrations of any clinician rated interview based scale such as CGAS, CDRS-R, MADRS, HAM-D
	MD, MA, MS, MSW, RN, BS, BA	≥1 year clinical experience with pediatric population and/or pediatric clinical trial experience	5 administrations of any clinician rated interview based scale
CGI	Child and Adolescent or Psychiatrist (or in the case of countries outside the US, the local country equivalent in education and training) or Adult Psychiatrist, (PI or SubI) or Doctoral Level Psychologist	≥1 year clinical experience with pediatric population and/or pediatric clinical trial experience	5 administrations of the CGI or similar type global rating scale such as CGIC
CDRS-R/CGAS	Child and Adolescent or Psychiatrist (or in the case of countries outside the US, the local country equivalent in education and training) or Adult Psychiatrist; or Doctoral Level Psychologist	≥1 year clinical experience with pediatric population and/or pediatric clinical trial experience	5 administrations of any clinician rated interview based scale such as YMRS, HAM-D, MADRS, CDRS-R or CGAS
	MD, MA, MS, MSW, RN, BS, BA	≥1 year clinical experience with pediatric population and/or pediatric clinical trial experience	5 administrations of any clinician rated interview based scale
K-SADS	Child and, Adolescent Psychiatrist (or in the	≥1 year clinical experience with pediatric	5 administrations of any diagnostic interview based

Rating Scale	Educational Level*	Prior Clinical and Pediatric Experience	Prior Scale Experience
	case of countries outside the US, the local country equivalent in education and training) or Adult Psychiatrist (PI or SubI) or Doctoral Level Psychologist	population and/or pediatric clinical trial experience	scale such as SCID, MINI, MINI-KID, DIS, CIDI
AIMS/BARS/SAS	Child and Adolescent Psychiatrist (or in the case of countries outside the US, the local country equivalent in education and training) or Adult Psychiatrist or other physician	≥1 year clinical experience with pediatric population and/or pediatric clinical trial experience	5 administrations of any movement scale such as AIMS/BARS/SAS or ESRS-A, UPDRS or the Global Dystonia Scale

* International equivalencies will be accepted. Doctoral level psychologist (PhD or PsyD) must be trained in child development.

** Upon 2 year expiration of documented certification, raters will be required either to retake C-SSRS training or resubmit valid, current documented certification. Should the two years lapse during the course of the study, retraining updated training and a renewed certificate will be required.

1. AMENDMENTS FROM PREVIOUS VERSIONS

- Added subgroup analysis section.

2. INTRODUCTION

Note: In this document any text taken directly from the protocol (A121201 protocol amendment 1 dated 19February2019) is italicized.

This protocol describes a 6-month, open label extension study (A1281201) of the A1281198 study. The purpose of adding this extension study to the ongoing Geodon pediatric bipolar program is to obtain additional longer term safety data in children and adolescents with Bipolar I disorder treated with ziprasidone.

Studies A1281198 and A1281201 are being conducted to fulfill a Pediatric Research Equity Act (PREA) commitment to assess the safety and effectiveness of Geodon® (ziprasidone) as a treatment for bipolar disorder in pediatric patients 10 to 17 years of age, which was issued by the United States (US) Food and Drug Administration (FDA) to Pfizer in August 2004.

[figure not shown]
Ziprasidone is an atypical antipsychotic with a high affinity for the dopamine D2 receptor and the 5-Hydroxytryptamine Receptor 2A (5-HT2A) receptors. It blocks re-uptake of serotonin and norepinephrine and exhibits 5-Hydroxytryptamine Receptor 1A (5-HT1A) agonist activity. The indication for this study is pediatric Bipolar I Disorder. The study will include out-patient and/or inpatient, male and female subjects aged 10-17 (inclusive) who meet the Diagnostic and Statistical Manual of Mental Disorders Fifth Edition (DSM V) diagnostic criteria for Bipolar I Disorder (current or most recent episode manic) and who participated in Study A1281198.

2.1. Study Design

This 26 week open label extension study is designed to provide information on the safety and tolerability of oral ziprasidone (20 to 80 mg BID with meals) during long term administration in children and adolescents with Bipolar I Disorder (current or most recent episode manic). It will enroll subjects who have participated in the 4 week, double blind, placebo controlled safety and efficacy trial, Study A1281198, meet study entry criteria, and wish to receive treatment with open label ziprasidone.

The number of subjects entering this open-label trial will be determined by the number of subjects electing to continue treatment after completing or withdrawing from the preceding double blind Study A1281198. We estimate that approximately 55 subjects randomized in the double blind study (based on the increased sample size of N=194 subjects) will be eligible to continue in this open label extension. With an expected dropout rate of approximately 35%, this gives an estimate of approximately 40 subjects to complete this 26 week open label study (if all 55 subjects enter the extension study).

The final visit of the double blind trial (Week 4 or early termination visit from A1281198) will serve as the Baseline Visit for the extension study. The first 1-14 days of Study A1281201 will be considered a transition period during which the study drug will continue to be administered under double-blind conditions. During this double-blind transition period, subjects who were on placebo in Study A1281198 will be provided active medication that will allow them to be titrated up to the appropriate weight-adjusted target dose, following titration schedule that was employed in Study A1281198. Subjects who were on active medication (ziprasidone) at the end of Study A1281198 will continue on that treatment course under double-blind conditions. At the end of the double-blind transition period, all subjects will receive open label ziprasidone.

Any subject who cannot tolerate the transition study medication during Week 1 should be discontinued from the study.

After the Week 2 visit for the ≥ 45 kg subjects and after the Week 1 visit for the <45 kg subjects, dosing will be open label and flexible, with dosing adjustments made at the discretion of the investigator to maintain optimal efficacy and tolerability. For subjects with a body weight of ≥ 45 kg, the target dose range is a total daily dose of 120-160 mg/day given in two divided doses with food. For subjects with a body weight <45 kg, the target dose range is a total daily dose of 60-80 mg/day given in two divided doses with food.

Subjects who cannot tolerate a dose of 80 mg/day will be allowed to have a dose reduction and to continue study treatment at a lower dose that is tolerable to them. The minimum permitted dose is 40 mg/day (20 mg BID) for all subjects.

Post Baseline visits will occur at Weeks 1, 2, 4, 6, 10, 14, 18, 22 and 26 during treatment, with a follow up visit at Week 27.

2.2. Study objective

To assess the safety and tolerability of oral ziprasidone (20-80 mg BID) during long term, open label administration in children and adolescents with Bipolar I Disorder who participated in Study A1281198.

2.3. Allocation to Treatment

Throughout most of this study, ziprasidone will be administered as open label (OL) investigational product to all subjects. However, the dose transition from the double-blind study drug administered in Study A1281198 to the open-label dosing in the extension trial A1281201 will be conducted under double-blind conditions.

The double-blind dose transition phase of Study A1281201 will comprise Weeks 1 and 2 for subjects ≥ 45 kg and Week 1 for subjects < 45 kg. The double-blind (DB) medication for this transition period will be assigned according to the subject's randomization number in the preceding study so that the investigator remains blinded during this period.

At the baseline visit of the A1281201 study, subjects will transition onto active medication if previously assigned to the placebo group or continue on active study drug. Over the course of the double-blind dose transition period, subjects < 45 kg will be transitioned to a total daily dose of 60 mg a day by Day 7 of Week 1 and subjects ≥ 45 kg will be transitioned to a total daily dose of 120 mg a day by Day 10 of Week 2. All medication will remain blinded until the end of the transition period.

3. ENDPOINTS AND BASELINE VARIABLES AND CONVENTIONS

For collection schedules for all endpoints, please refer to the protocol.

3.1. Efficacy Endpoints

- *Young Mania Rating Scale (YMRS).*
- *Clinical Global Impression of Severity (CGI-S).*
- *Children's Global Assessment Scale (CGAS).*

3.2. Special Safety Endpoints

- *Child Depression Rating Scale - Revised (CDRS-R).*
- *Columbia Suicide Severity Rating Scale (C-SSRS).*
- *Movement Disorder Scales (SARS, BAS, and AIMS).*

3.3. Safety Endpoints

- *Adverse event reporting;*
- *Clinical laboratory testing;*

- *Physical examinations;*
- *Blood pressure and pulse;*
- *Height and weight;*
- *Body Mass Index (BMI) and BMI Z score;*
- *Waist circumference;*
Electrocardiograms, including QTc.

3.4. Baseline Variables

No baseline covariates in the planned analysis.

Baseline visit for the open-label extension study will be the final visit of the double blind trial (Week 4 or early termination visit from A1281198), except for safety ECG parameters. For ECG parameters, baseline values will be the value from the Baseline visit in the double-blind study A1281198.

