The blister cards for Weeks 3-26 will each contain medication for 8 days. Two blister cards will be dispensed at Weeks 2 and 4 and then 4 blister cards will be dispensed at each monthly visit from the Weeks 6 visit through the Week 22 visit. Dose increases should be limited to 20 mg a week during Weeks 6-22 of the flexible dosing weeks of the study. However, subjects ≥ 45 weight can be increased to 160 mg a day after they have been on a stable dose of 120 mg a day if clinically indicated. [Table 1](#), [Table 2](#), [Table 3](#) and [Table 4](#) provide the dose transition schedule for all possible dose levels for subjects in both weight categories.

Statistical Methods:

Sample Size

The number of subjects entering this open-label trial will be determined by the number of subjects electing to continue treatment after completing or withdrawing from the preceding double blind study, A1281198. We estimate that approximately 55 subjects randomized in the double blind study (based on the increased sample size of N (number) =194 subjects) will be eligible to continue in this open label extension. With an expected dropout rate of approximately 35%, this gives an estimate of approximately 40 subjects to complete this 26 week open label study (if all 55 subjects enter the extension study).

Data Summarization Methods

As this is an open label study with no comparator, no inferential statistics will be performed. Quantitative variables will be described by standard descriptive statistics (n, mean, standard deviation, minimum, and maximum, 95% confidence intervals), and qualitative variables will be summarized by frequency tables. Summaries will include data for all subjects who took at least one dose of investigational product in this open label extension study.

Baseline values for efficacy, outcomes and special safety endpoints will be the last observation made prior to the subject's receiving open label treatment. For safety, for those subjects who were randomized to placebo in the double blind study, baseline values will be

the last observation prior to initiating dosing in the open label extension study (normally, the observation of the last visit in the double blind study); and for those subjects who were randomized to ziprasidone in the double blind study, baseline values will be the last observation prior to initiating dosing in the double blind study (normally, the value from the Baseline visit in the double blind study).

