9. DATA ANALYSIS/STATISTICAL METHODS

Detailed methodology for summarization of the data collected in this trial will be documented in a Statistical Analysis Plan (SAP). The SAP may modify the plans outlined in the protocol; however, any major modifications of significant change to the primary endpoint definition and/or its analysis will also be reflected in a protocol amendment.

As this is an open label study with no comparator, no inferential statistics will be performed. Quantitative variables will be described by standard descriptive statistics (n, mean, standard deviation, minimum, and maximum, 95% confidence intervals), and qualitative variables will be summarized by frequency tables. Summaries will include data for all subjects who took at least one dose of investigational product in this open label extension study.

Baseline values for efficacy, outcomes and special safety endpoints will be the last observation made prior to the subject receiving open label treatment. For safety, for those subjects who were randomized to placebo in the double blind study, baseline values will be the last (pre dose, for ECG and blood pressure/pulse only) observation prior to initiating dosing in the open label extension study normally, the (pre dose, for ECG and blood pressure/pulse only) observation of the last visit in the double-blind study; and for those subjects who were randomized to ziprasidone in the double blind study, baseline values will be the last observation prior to initiating dosing in the double blind study (normally, the value from the Baseline visit in the double blind study).

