4. ANALYSIS SETS (POPULATIONS FOR ANALYSIS)

4.1. Safety Analysis Set

As the objective of the study is long-term safety and tolerability of ziprasidone, only one analysis set, “Safety Analysis Set” defined below will be used for data summaries.

The Safety Analysis Set (SAS) will include *all subjects who took at least one dose of study medication in this open-label extension study.*

All summaries will be based on the “as reported” visits (as recorded on the Case Report Forms).

For data summary purposes, subjects will be classified into one of the following two groups:

- Ziprasidone/Ziprasidone: randomized to ziprasidone in the preceding double-blind study (and on ziprasidone in the current open-label extension study).
- Placebo/Ziprasidone: randomized to placebo in the preceding double-blind study (and on ziprasidone in the current open-label extension study).

In addition, the above two groups will be combined as:

- Combined: combination of the two groups Ziprasidone/Ziprasidone and Placebo/Ziprasidone. This is essentially the set of all subjects in the current open-label extension study.

Data summaries will be done based on Ziprasidone/Ziprasidone and Placebo/Ziprasidone, as well as Combined.

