6.5.2. Laboratory Data

All clinical laboratory data will be displayed in listings grouped by type of laboratory test (eg, hematology, blood chemistry) for each sample collection date. Values outside of the normal range will be noted; the respective normal high or low value will be presented in parentheses, linked to the abnormal laboratory value. Laboratory values will be summarized as median changes from baseline and also by frequency of occurrence of clinically significant abnormal values.

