6.5.4. Body Weight and Height, BMI, Waist Circumference

Data for height, weight, BMI, and waist circumference will be summarized by time point using descriptive statistics. Additionally, height, weight, and BMI will be standardized using CDC (Child Development Chart) growth charts and the resulting z scores presented in listings and frequency tables in 1 unit intervals. In addition, frequency tables of above/below a 1 point increase in the z scores for BMI will be presented.

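### SAP 3.4 gives prior-ziprasidone subjects an on-drug baseline for laboratory change and the BMI z-score increase, where the protocol sets a pre-drug one; its ECG baseline for prior-placebo subjects also departs from the protocol

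*SAP*

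**What the plan says.** Protocol section 9 splits the safety baseline by treatment in the preceding study. For subjects randomized to ziprasidone, "baseline values will be the last observation prior to initiating dosing in the double blind study". For subjects randomized to placebo it is the last value before the extension starts, worded as "pre dose, for ECG and blood pressure/pulse only) observation prior to initiating dosing in the open label extension study". The Protocol Summary, under Statistical Methods, repeats the split: "for those subjects who were randomized to ziprasidone in the double blind study, baseline values will be the last observation prior to initiating dosing" (meaning A1281198 dosing). For efficacy and special safety scales, section 9 uses the last value before open-label treatment, whatever the prior arm.

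SAP 3.4 has no split: "Baseline visit for the open-label extension study will be the final visit of the double blind trial". It makes one exception: "For ECG parameters, baseline values will be the value from the Baseline visit in the double-blind study A1281198".

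The SAP outputs that depend on this choice are:
- SAP 6.5.2: "Laboratory values will be summarized as median changes from baseline".
- SAP 6.5.4: "frequency tables of above/below a 1 point increase in the z scores for BMI will be presented".
- SAP 6.5.6: mean ECG change and categorical QTc increases from baseline.

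All are shown by prior-treatment group and pooled ("Combined: combination of the two groups Ziprasidone/Ziprasidone and Placebo/Ziprasidone", SAP 4.1).

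Protocol 7.2 adds a further ECG statement, taking baseline ECG data from the last A1281198 visit for all subjects.

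**The concern.** A Ziprasidone/Ziprasidone subject reaches the final A1281198 visit after weeks on ziprasidone. If that visit is the reference, a change in prolactin, a fasting metabolic test or BMI z-score that arose in those weeks and persisted becomes part of the baseline and is not counted. A marker that rose early and then recovered would appear as a fall. The Combined column would pool these changes with Placebo/Ziprasidone changes measured from a drug-free value.

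Safety and tolerability are the study's only objective, and laboratory tests, BMI z-score and ECG all stand under primary endpoints in protocol section 2. A programmer following the SAP and a reader following the protocol would obtain different results under the same label, change from baseline.

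**Working it through.** **Step 1. Set the rules side by side.**

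| Endpoint and group | Protocol section 9 | SAP 3.4 | Result |
|---|---|---|---|
| Laboratory, BMI z-score; Ziprasidone/Ziprasidone | Before first double-blind dose (pre-drug) | Final A1281198 visit (on drug) | Conflict |
| Laboratory, BMI z-score; Placebo/Ziprasidone | Before first extension dose | Final A1281198 visit | Agree |
| ECG; Ziprasidone/Ziprasidone | Before first double-blind dose | A1281198 Baseline visit | Agree |
| ECG; Placebo/Ziprasidone | Last pre-dose value before the extension | A1281198 Baseline visit | Conflict; both drug-free |
| Efficacy and special safety scales; both groups | Last value before open-label treatment | Final A1281198 visit | Agree |

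Protocol 7.2 (final A1281198 visit for every ECG) matches section 9 for Placebo/Ziprasidone but not for Ziprasidone/Ziprasidone. It differs from SAP 3.4 in both groups.

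**Step 2. Identify the outputs affected.** Median laboratory change uses baseline expressly. The BMI z-score table does not name its reference, but an increase needs one, and SAP 3.4 exempts only ECG. Adverse events, listed vital signs and the by-time-point height, weight, BMI and waist summaries are not materially affected.

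**Step 3. How much time on drug precedes the SAP baseline.** The plan gives no figure to reproduce. Let w be the double-blind weeks on ziprasidone and t the extension week. The share is w/(w + t).

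Inputs:
- w = 4: full length of A1281198 (protocol section 3).
- w = 3: usual minimum (protocol 4.1, inclusion criterion 3).
- w = 2: an assumption for the insufficient responders whom criterion 3 admits earlier; the A1281198 titration length is not given.
- t = 6 and 26 for laboratory tests, with fasting tests also at 18 (protocol 7.1.2). Body measurements are at 6 and 26 (protocol 7.1.5).

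| w | Week 6 | Week 18 | Week 26 |
|---|---|---|---|
| 4 | 4/10 = 40.0% | 4/22 = 18.2% | 4/30 = 13.3% |
| 3 | 3/9 = 33.3% | 3/21 = 14.3% | 3/29 = 10.3% |
| 2 (assumed) | 2/8 = 25.0% | 2/20 = 10.0% | 2/28 = 7.1% |

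**Step 4. Effect on the 1-point threshold (illustration only).** If a fraction f of a subject's total BMI z-score rise comes before the final A1281198 visit, the SAP sees (1 − f) of it. The total rise needed to count is then 1/(1 − f): 1.15 for f = 4/30, 1.33 for f = 0.25 and 2.00 for f = 0.50. Under the protocol rule it is 1.00 throughout. As an invented example, take values of 0.0 pre-drug, 0.3 at extension entry and 1.1 at Week 26. The protocol change is 1.1 − 0.0 = 1.1, which counts. The SAP change is 1.1 − 0.3 = 0.8, which does not.

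**The case against.** The SAP states its rule openly, and protocol section 9 allows the SAP to modify the protocol's plans. That stands, but the SAP neither flags the rule as a departure nor gives a reason. Section 9 also says that major changes to a primary endpoint's definition or analysis go into a protocol amendment. Whether or not this change counts as major, it should be declared.

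Extension entry can be a legitimate baseline for an extension study. That also stands; the defect is two unreconciled rules under one label.

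The bias is not quantified, and protocol 1.2.1 reports neutral weight, glucose and lipid effects in adults with mania. It is true that no bias can be sized. The shares above are of time, not dose or effect, and early weeks may include lower titration doses. But the adult statement does not cover prolactin, and this study exists to collect paediatric safety data.

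The ECG conflict is milder. Both candidate values for Placebo/Ziprasidone precede any ziprasidone, so the argument about understated effects does not apply to QTc. This is accepted: it is a consistency defect.

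For the scales, open-label treatment could be read literally as starting after the blinded transition, which would put baseline at Week 1 or 2. The natural reading is the final A1281198 visit, which protocol section 3 names as the extension's Baseline Visit.

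Finally, the analyses are descriptive, and clinically significant laboratory abnormalities are also counted. This limits the consequence but leaves the change tables wrong against the protocol.

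**Conclusion.** The concern holds. SAP 3.4 contradicts protocol section 9 for laboratory change and the BMI z-score increase in Ziprasidone/Ziprasidone, and so in Combined. It also contradicts section 9 for ECG change in Placebo/Ziprasidone. Confidence in the textual conflict is high.

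For Ziprasidone/Ziprasidone, the time on drug left before the SAP baseline is about 25% to 40% of the total at Week 6 and 7% to 13% at Week 26. The lower ends rest on the assumed 2-week case. The effect on the results could be small or large, and the documents do not allow it to be estimated. This should be fixed before the tables are programmed; it does not threaten the study's design.

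**What to change.** Rewrite SAP 3.4 by group and endpoint class, following protocol section 9:
- **Safety endpoints of SAP 3.3 that use a baseline, Ziprasidone/Ziprasidone:** last observation before the first A1281198 dose.
- **The same endpoints, Placebo/Ziprasidone:** last observation before the first extension dose, pre-dose for ECG and blood pressure/pulse. State that this changes the SAP's current ECG baseline for this group.
- **Efficacy and special safety scales:** keep the extension-entry value.
- **Subjects reclassified under SAP 4.2:** state which baseline they take, since section 9 is worded by randomized arm and SAP 4.2 by treatment received.

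Reconcile protocol 7.2 with section 9 and the SAP on the ECG baseline. Change from extension entry in Ziprasidone/Ziprasidone may be added as a supportive summary. If the sponsor prefers the present SAP rule, it should say so, justify it and align protocol section 9.

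The cost is wording and one derived variable, with no new procedures or patients. The fix needs A1281198 Baseline values, and that study's schedule is not in the documents. Any test not measured then would have no change from baseline in Ziprasidone/Ziprasidone. Time on drug at a given visit would also differ between groups (with 4 double-blind weeks, 4 + 26 = 30 against 26 weeks at Week 26), which a table footnote should state.
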